## 5 TREATMENTS

### 5.1 Study treatment

Study treatments include ACT-334441 and matching placebo, which are administered during a 12-week double-blind treatment period.

#### 5.1.1 Investigational treatment: description and rationale

ACT-334441 is supplied as capsules at the doses of 0.5 mg, 1 mg, 2 mg, or 4 mg. The matching placebo is supplied as identical capsules formulated with the same excipients but without the active ingredient, ACT-334441.

The four treatment doses of 0.5 mg, 1 mg, 2 mg, or 4 mg were selected based on PK, PD, safety, and tolerability results from the Phase 1 study, where such doses were administered o.d. up to 35 days in healthy subjects [see Section 1.3.2].

Inactive ingredients of ACT-334441 formulation are: methycellulose, sodium lauryl sulfate, mannitol, colloidal silicon dioxide and dipalmitoylphosphatidylcholine; the capsule shell contains hydroxypropylmethylcellulose and titanium dioxide.

#### 5.1.2 Study treatment administration

One capsule of ACT-334441 or placebo will be taken orally irrespective of food intake. The capsule will be swallowed as a whole. It is preferable that the capsule be taken each day at approximately the same time (preferably each morning).

On the day of the study visits, study drug must be taken only after the completion of the pre-dose safety assessments (SBP, DBP, ECGs, PFTs, laboratory tests) and PK sampling.

#### 5.1.3 Treatment assignment

In Part A, a total of 48 eligible subjects will be randomized in a 1:1:1:1 ratio to ACT-334441 0.5 mg, 1 mg, and 2 mg or placebo. In Part B, a total of 16 eligible subjects will be randomized in a 3:1 ratio to ACT-334441 4 mg or placebo.

Each of the clinical study sites will be assigned a unique site number. At Visit 1 (Screening), all screened subjects will be assigned a study-specific subject number by the IRT system, which identifies the subject throughout the study. After having confirmed

the eligibility of the subject and prior to the start of study treatment, the investigator/delegate contacts the IRT system at Visit 2 to randomize the subject. The IRT system assigns a randomization number to the subject and assigns the bottle number that matches the treatment arm assigned by the randomization list to the randomization number.

The randomization list is generated by the independent IRT provider and is kept strictly confidential.

#### **5.1.4 Blinding**

##### ***5.1.4.1 Study drug material related blinding***

This study will be performed in a double-blind fashion. The investigator and study staff, the subjects, the clinical research associates (CRAs), all Clinical Trial Team (CTT) members at Actelion and Contract Research Organizations (CROs) involved in the conduct of the study will remain blinded to the treatment allocation until study closure. Actelion staff responsible for clinical trial supply will need to be unblinded to ensure adequate distribution of study treatment. These persons will be clearly identified, their unblinding will be documented in the trial master file, and they will not take part in any CTT meetings after the study set-up has been completed.

Until the time of unblinding for final data analysis, the randomization list is kept strictly confidential and accessible only to authorized persons who are not involved in the conduct and analysis of the study [see Section 5.1.5]. A sealed randomization code is kept by Actelion Global Quality Management in a safe cabinet. A second set will be provided to the statistician of the Independent Statistical Analysis Center (ISAC) for the production of unblinded IDMC statistical outputs.

The investigational treatment and its matching placebo are indistinguishable, and all bottles will be packaged in the same way.

##### ***5.1.4.2 Functional blinding***

First-dose effects on HR and AV conduction and lymphocyte counts reduction have been identified as potentially unblinding information. Access to this information by the site's staff and sponsor's study team will be restricted.

The following measures will be taken to ensure that the main site staff and the Actelion study team will remain blinded to lymphocyte counts and that the medical review of cardiac safety assessments with unblinding potential will be performed without introducing bias:

- Results of the total WBC count and total lymphocyte count will not be communicated to the sites, sponsor, and CRO unless a total lymphocyte count

< 200 cells/ $\mu$ L at any study visits until EOT or < 800 cells/  $\mu$ L at EOS, is recorded by the central laboratory. In these events an alert will be sent to the principal investigator and to the sponsor including lymphocyte count results. Follow-up monitoring must be provided as described in Section 5.1.10.2.

- Blood samples for lymphocyte subset exploratory analysis will be analyzed by the sponsor within 6 days after sampling. In order to avoid potential unblinding, the blood samples will be shipped to Actelion via the central laboratory with scrambled identification numbers. The Actelion team performing the analysis will be separated from the Actelion study team and will not have access to the subject number, date and time of the sampling (i.e., baseline or EOT) prior to database lock.
- At the site level:
  - A CSA will perform and evaluate the cardiac safety assessments on Day 1 (Randomization) and on days of study treatment re-initiation.
  - The subject will be instructed not to discuss any results related to the first-dose administration (i.e., ECG results) with the principal investigator / treating physician or any other blinded site personnel.
  - The central reading reports on 12-lead ECG and 24-hour Holter ECG performed after first dosing will be sent to the CSA only and must not be shared with the principal investigator / treating physician.
  - The principal investigator / treating physician and the CSA must not discuss any issues related to subject care and management on Day 1 or first day of study drug re-initiation, unless mandated for subject safety reasons. The principal investigator should not access the blinded ECG results, unless medically mandated to ensure subject's safety.
- At the sponsor level:
  - The medical review of all first-dose data assessed on Day 1 (Randomization) or on days of study treatment re-initiation (including hourly post-dose 12-lead ECGs and 24-hour Holter ECG data with unblinding potential, as well as other relevant data) will be performed by a first-dose monitor. He/she will only discuss the first-dose data with the CSA, the site CRA and/or IDMC members. Further details on the role of the first-dose monitor are described in the first-dose monitor charter.
  - Other sponsor team members involved in the medical review of other study data will not have access to first-dose data.

## **5.1.5 Unblinding**

### ***5.1.5.1 Unblinding for final analyses***

Full randomization information will be made available for data analysis only after database closure in accordance with Actelion standard operating procedures (SOPs).

### ***5.1.5.2 Unblinding for interim analyses***

An ISAC, not otherwise involved in the design, conduct and analysis of the study, will have access to the randomization code in order to prepare the interim analysis reports and unblinded periodic reports for review by the IDMC during the course of the trial. The randomization code will be made available to the ISAC in accordance with the sponsor's SOPs.

### ***5.1.5.3 Unblinding before final analyses***

The randomization code will be made available to the PK bioanalytic laboratory in accordance with the sponsor's SOPs.

### ***5.1.5.4 Unblinding for suspected unexpected serious adverse reactions***

When a suspected unexpected serious adverse reaction (SUSAR) occurs for a subject participating in the study, Actelion Global Drug Safety will request the unblinding of the treatment assignment. The randomization code will not be communicated to the site staff or to the Actelion study team; unblinded SUSAR information will be anonymized and provided to Actelion Global Drug Safety, respective health authorities and Institutional Review Boards (IRBs) / Independent Ethics Committees (IECs), and the IDMC. SUSARs will be reported to investigators in a blinded fashion.

### ***5.1.5.5 Emergency procedure for unblinding***

The investigator, study staff and sponsor staff must remain blinded to the subject's treatment assignment. The identity of the study treatment may be revealed only if the subject experiences a medical event, the management of which would require knowledge of the blinded treatment assignment. In this case, the investigator can receive the unblinded randomization code for study treatment allocation through the IRT system. In these situations, the decision to unblind resides solely with the investigator. Whenever it is possible and if it does not interfere with (or does not delay) any decision in the best interest of the subject, the investigator should discuss the intended code break with the sponsor.

The occurrence of any code break during the study must be clearly justified and explained by the investigator. The investigator must not disclose the unblinded treatment in the eCRF or to the sponsor or its delegates. In all cases, the sponsor must be informed as soon as possible before or after the code break.

The circumstances leading to the code break must be documented in the site study file and eCRF.

Refer to the IRT system guidelines for complete information regarding the IRT system procedures for randomization, study drug assignment, and unblinding.

### **5.1.6 Study treatment supply**

Manufacture, labeling, packaging and supply of study treatments will be conducted according to Good Manufacturing Practice, Good Clinical Practice (GCP) and any local or national regulatory requirements.

All treatment supplies are to be used only in accordance with this protocol and not for any other purpose.

#### ***5.1.6.1 Study treatment packaging and labeling***

##### *5.1.6.1.1 Study treatment packaging and preparation*

Study treatment (ACT-334441 or placebo) is provided as capsules and is supplied in childproof bottles.

##### *5.1.6.1.2 Study treatment labeling*

Study treatment is labeled to comply with the applicable laws and regulations of the countries in which the study sites are located.

The batch number and the retest date (or expiry date) will be given on the study treatment labels.

#### ***5.1.6.2 Study treatment distribution and storage***

Treatment supplies must be kept in an appropriate, secure area and stored according to the conditions specified on the medication labels.

#### ***5.1.6.3 Study treatment dispensing***

The subjects will receive sufficient study treatment to cover the period up to the next scheduled visit. Subjects are asked to return all used, partially used and unused study treatment bottles at each visit. The protocol-mandated study drug dispensing/return procedures may not be altered without prior written approval from the sponsor. An accurate record of the date and amount of study treatment dispensed to each subject must be available for inspection at any time.

#### ***5.1.6.4 Study treatment return and destruction***

On an ongoing basis and/or upon termination of the study, the CRA will collect used and unused subject kits, which will be sent to the warehouse, where the sponsor or a representative will check treatment reconciliation. In certain circumstances, used and

unused treatment bottles may be destroyed at the site once treatment accountability is finalized and checked by the sponsor or a representative, and written permission for the destruction has been obtained from the sponsor

If the CRA is not able to reconcile the treatment due to lost or prematurely destroyed bottles prior to destruction, the site is to provide detailed documentation that describes the loss or premature destruction to justify treatment accountability.

### **5.1.7 Study treatment accountability and compliance with study treatment**

#### **5.1.7.1 Study treatment accountability**

The inventory of study treatment dispensed and returned (i.e., study treatment accountability) must be performed by the study staff on the day of the subject visit and before providing further study treatment. It is recorded on the investigational medicinal product dispensing and accountability log and in the eCRF and checked by the CRA during site visits and at the end of the study. The study treatment accountability log in the eCRF will include at least the following information for each study treatment bottle dispensed to the subject:

- Dispensed bottle number
- Date dispensed / number of capsules dispensed (pre-populated in eCRF)
- Date returned / number of capsules returned

All study treatment supplies, including partially used or empty bottles, must be retained at the site for review by the CRA.

If the subject forgets to bring the remaining study treatment to a study visit, he/she must be instructed to not take any tablet/capsules from the remaining study treatment and to bring it to the next visit.

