- (5) On Day 1 and at re-initiation, SBP/DBP assessment and 12-lead ECG will be done pre-dose and hourly until 6 h post-dose; after 6 h, subjects may be discharged from the hospital if they meet the discharge criteria, otherwise SBP/DBP assessments and 12-lead ECG will be performed hourly until discharge criteria are met. If discharge criteria are not met after 12 h, the subject must be permanently discontinued. At all other visits, only pre-dose SBP/DBP assessments and 12-lead ECG will be performed.
- (6) At Screening, SBP/DBP will be assessed in supine position and after 1 to 3 minutes in standing position to assess orthostatic hypotension. At all other visits, SBP/DBP will be assessed in supine position.
- (7) At Screening, 24 hour ECG-Holter will start before 12:00. On Day 1, 24 hour ECG-Holter will start immediately before dosing.
- (8) Two spirometry assessments will be performed at Visit 1 (Screening). The assessments should be at least 5 days apart. The last assessment will count as baseline.
- (9) Hematology assessments including coagulation tests will be performed at each visit until EOS
- (10) Serum pregnancy tests will be performed at Screening and EOS. Urine pregnancy tests will be performed at all other visits (including telephone calls FU, 11 weeks and 16 weeks after study treatment discontinuation).
- (11) IgM, IgG, IgA, CRP, fibrinogen, and BLyS will be measured in serum. At Randomization visit only, anti-Smith, anti-cardiolipin, and anti-ribosomal P will also be measured. EDTA plasma samples will be shipped via central laboratory to Actelion for analysis of CXCL10 and other soluble biomarkers potentially related to SLE and/or S1P1 modulation.
- (12) Blood samples will be shipped via central laboratory to Actelion for lymphocyte subsets analysis.
- (13) No study drug dispensing at V3 and re-initiation visit
- (14) All AEs and SAEs that occur after signing the Informed Consent Form and up to 6 weeks (AEs) or 16 weeks (SAEs) after study treatment discontinuation must be reported.
- (15) Prior to randomization, the following central laboratory results must be available to confirm eligibility: ANA, anti-dsDNA, Hepatitis B surface antigen, Hepatitis C, HIV1 and HIV2, varicella-zoster virus, urine protein-to-creatinine ratio, ALT/AST/TBIL, pregnancy test (if applicable).
- (16) EOT visit should preferably take place 1 day after last study treatment dose, and no later than 7 days.

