**Accountability based compliance =**

$$\left[ \frac{\text{[(number of capsules dispensed at Visit } n - \text{ number of capsules returned at Visit } n+1)]}{\text{number of capsules that should have been taken during the period*}} \right] \times 100$$

\*The period is defined as the number of days elapsed between the respective visits.

During the study, study treatment compliance based on accountability is expected to be above 80%. If below 80%, without a medical justification (e.g., adverse event), this will be considered as a protocol deviation. The investigator must check with the subject the

reasons for this non-compliance and discuss actions to be taken to avoid re-occurrence at the next visit. If the subject forgets to bring the remaining study treatment to a study visit, he/she will be asked to bring it to the next visit.

At Visit 3 and re-initiation visits, a compliance review based on study drug accountability, will be performed by the investigator (or delegate) and recorded in the eCRF.

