### **5.1.8 Study treatment interruptions**

Study treatment should not be interrupted. If study treatment intake is interrupted by the subject for a day or more for any reason, she/he must immediately inform the principal investigator / treating physician. If a subject forgets to take study treatment in the morning, she/he should take it on the same day and resume regular dosing the next morning.

The following guidance is provided for re-initiation of study treatment after study treatment interruptions.

Note that under no circumstances should a subject take more than one capsule per day.

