### ***8.2.1.2 Visit 2 – Day 1 – Randomization and post-dose assessment***

After confirmation of eligibility (i.e., verification of all entry criteria) by the investigator, randomization should occur via IRT to obtain randomization and study treatment kit numbers. Study treatment should then be dispensed and the subject should take the first dose of study treatment.

Visit 2 post-dose assessments include:

- Hourly 12-lead ECG and SBP/DBP assessments for 6 hours or until the patient meets the discharge criteria (under the responsibility of the CSA [see [Appendix 4](#)]). If discharge criteria are not met after 12 hours, the subject should be permanently discontinued.
- Recording of AEs and SAEs.

The subject will be instructed to contact the site if she/he has any questions or problems. WOCBP will be reminded to use the methods of contraception defined for this study. The reminders must be documented in the hospital chart.

An appointment for next visit will be scheduled and the subject will be instructed to:

- bring back the remaining study medication for drug accountability
- come fasted to the site
- not take study treatment on the day of study visit prior to coming to the site
- contact the principal investigator / treating physician immediately in the event of the appearance of any symptoms (e.g., suggestive of an SLE flare) or any AEs or SAEs or if a study treatment dose is missed.

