### **8.2.2 Visit 3 – Week 2**

The time window for this visit is  $\pm 3$  days. The date of the visit will be registered by the investigator or study staff in the eCRF only (no IRT visit registration as no study drug dispensing at Visit 3). All assessments may be performed up to 3 days prior to or after this visit date. The visit includes:

- Recording of change in concomitant medications and background SLE therapies since Visit 2
- Recording of methods of contraception (for WOCBP)
- Abbreviated physical examination
- SBP/DBP
- 12-lead ECG
- Spirometry (under the responsibility of the pulmonary function laboratory technician or expert)
- Ophthalmological examination (under the responsibility of the ophthalmologist)

- Hematology (including coagulation tests), blood chemistry
- Urine pregnancy test (for WOCBP)
- Urinalysis
- PK sampling
- Study drug accountability for compliance review
- Recording of AEs and SAEs
- Remind WOCBP to use the methods of contraception defined for this study
- Schedule an appointment for the next visit and instruct the subject to:
  - bring back any remaining study medication for drug accountability
  - come fasted to the site
  - not take study treatment on the day of study visit prior to coming to the site (study drug will be taken at the clinical site)
  - contact the principal investigator / treating physician immediately in the event of the appearance of any symptoms (e.g., suggestive of an SLE flare) or any AEs or SAEs or if a study treatment dose is missed.

### 8.2.3 Visit 4 – Week 4 and Visit 5 – Week 8

The visit window for these visits is  $\pm 5$  days. The date of study treatment dispensing, preferably corresponding to the date of registration of the visit in the IRT system defines the date of the visit. All other assessments may be performed up to 5 days prior to or after this visit date. The visit includes:

- Recording of changes in concomitant medications and background SLE therapies since previous visit
- Recording of methods of contraception (for WOCBP)
- Abbreviated physical examination
- SLEDAI-2K and PGA
- SBP/DBP
- 12-lead ECG
- Spirometry (under the responsibility of the pulmonary function laboratory technician or expert)
- Ophthalmological examination (under the responsibility of the ophthalmologist)
- Hematology (including coagulation tests) and blood chemistry
- Urine pregnancy test (for WOCBP)
- ANA, anti-dsDNA antibodies, complement C3 and C4
- Exploratory biomarkers
- Urinalysis
- PK sampling

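### The forgotten-bottle rule in Protocol 5.1.7.1 does not except Visit 3, where nothing is dispensed; followed as written it stops the subject's only supply, against 5.1.8

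*Protocol*

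**What the plan says.** Protocol Section 5.1.7.1 deals with counting capsules dispensed and returned. For a subject who comes without the remaining treatment, "he/she must be instructed to not take any tablet/capsules from the remaining study treatment and to bring it to the next visit". The trigger is any study visit. Section 5.1.6.3 sets the general expectation: "Subjects are asked to return all used, partially used and unused study treatment bottles at each visit".

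Visit 3 (Week 2) falls under this rule. At Visit 2 the subject is told, for the next visit, to "bring back the remaining study medication for drug accountability" and to "not take study treatment on the day of study visit prior to coming to the site" (Section 8.2.1.2). Section 5.1.7.2 confirms the purpose: "At Visit 3 and re-initiation visits, a compliance review based on study drug accountability, will be performed". But no drug is handed out. Table 1, footnote 13, reads "No study drug dispensing at V3 and re-initiation visit", and Section 8.2.2 gives the same reason for skipping the IRT: "no IRT visit registration as no study drug dispensing at Visit 3". The Visit 2 bottle therefore has to last until Visit 4.

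Section 5.1.8 opens with "Study treatment should not be interrupted" and says that a dose forgotten in the morning is taken later that day. The rules for missed doses then depend on timing:

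- **Days 1–14 (5.1.8.1):** one missed day means interruption and a monitored re-initiation visit within 7 days of the first missed dose, failing which the subject should be permanently discontinued. If the subject has already resumed without promptly reporting the miss, the investigator may continue treatment as planned.
- **After Day 14 (5.1.8.2, 5.1.10.8):** fewer than 7 consecutive missed days, dosing carries on; more than 7, permanent discontinuation.

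In the SAP, the PDS excludes a subject with an interruption documented in the first 21 days (Sections 4.1.1, 7.1.5.1, 11.2.2), and exclusion from the PDS brings exclusion from the PPS (Section 7.1.3).

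**The concern.** The instruction makes sense at a bottle exchange. The old bottle is at home, a new one is issued, and the subject should not draw from both. At Visit 3 there is no new bottle. Telling the subject to leave the old one alone until the next visit means telling the subject to stop treatment. A site cannot follow that instruction and also keep treatment uninterrupted as Section 5.1.8 asks.

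The timing matters. The stop would start around Week 2, when a single missed day may still call for a monitored restart, and inside the 21 days that the SAP requires to be free of documented interruption for the main pharmacodynamic analysis. An accountability rule could then by itself create the missed dose that the interruption rules are there to prevent.

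**Working it through.** The plan gives no figure on this point, so there is none to reproduce. The check is a comparison of visits followed by a day count.

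**1. What the rule does at each visit**

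| Visit | Bottle due for accountability | New bottle issued | Effect of the do-not-take rule |
|---|---|---|---|
| Visit 3 (Week 2) | yes | no | only supply stopped |
| Visits 4, 5 (Weeks 4, 8) | yes | yes | harmless |
| Visit 6 (EOT) | yes | no | harmless, dosing has ended |

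**2. When the stop would start.** SAP Table 11 sets the Week 2 target at Day 15, and the visit window is ±3 days (Protocol Table 1). Visit 3 is therefore on Days 15 − 3 = 12 to 15 + 3 = 18. If Week 2 is counted as Day 14, the range is Days 11 to 17. The subject arrives undosed and the bottle is at home, so under the literal rule the first missed dose is on the day of Visit 3 itself.

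**3. Stop starting on Days 12–14** (11–14 on the other count). One missed day is enough to bring in Section 5.1.8.1: interruption and a monitored re-initiation within 7 days, or else discontinuation. The exception is the subject who has already resumed without promptly reporting the miss. That path is narrow here, because the site gave the instruction and knows of it.

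**4. Stop starting on Days 15–18.** More than 7 consecutive missed days is reached on the 8th missed day, which is Day s + 7 for a stop starting on Day s.

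- s = 15: 15 + 7 = Day 22
- s = 18: 18 + 7 = Day 25

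The nominal Visit 4 is on Day 29, and 29 − 15 = 14 days separate the two target dates. An uncorrected stop could therefore pass the limit before Visit 4. If it is corrected in fewer than 7 days, dosing simply continues.

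**5. Analysis sets.** Every possible start day (11 to 18) is at or before Day 21. A stop entered in the study drug log as a temporary interruption (SAP Section 5.3.4) then fails the SAP definition of the PDS, and the PPS follows. Protocol Section 11.2.2 asks only for at least 3 weeks of treatment and one lymphocyte count between Weeks 4 and 12. A single missed day would not exclude the subject under that definition.

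**6. Size.** One affected subject is 1 of 12 in an active arm, or 8.3%. Protocol Section 11.6.1 already allows for 10% exclusions from the PDS, which is 0.10 × 12 = 1.2 subjects per active arm. The MCP-Mod and ANCOVA analyses are repeated on the FAS (SAP Section 10.6.4), which keeps every randomized subject.

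**The case against.** The best reply is that Section 5.1.7.1 was never meant for Visit 3. It speaks of taking inventory before more treatment is provided, and its neighbouring sentence on keeping partially used bottles at the site would, if applied at Visit 3, take the bottle from a subject who remembered it. Visit 3 is described separately as a compliance review. Section 5.1.7.2 repeats the forgotten-bottle case without the do-not-take clause, and Section 5.1.8 tells subjects to take a late dose the same day. Read together, these suggest that dosing continues from the current bottle. A sensible site would then lose no dose.

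As an account of intent, this is probably right. It does not remove the conflict. The instruction is a plain obligation for any study visit. Section 5.1.7.2 omits the clause but never says that dosing continues, and Section 5.1.8 does not qualify the obligation. Sections 5.1.6.3 and 13.5 discourage sites from varying return procedures or the protocol on their own judgment.

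Three stronger readings are tempting, and the documents do not support them:

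- **A forgotten bottle means a two-week gap and discontinuation.** The 14 days between target dates is the gap only if nobody corrects the error. Unscheduled visits are allowed at any time (Section 8.4).
- **Loss from the PDS is automatic.** It arises under the SAP definition, not the protocol's, and needs a logged interruption.
- **Re-initiation visits have the same defect.** Nothing is dispensed there either, but a subject without the bottle cannot take the monitored dose at that visit whatever Section 5.1.7.1 says.

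**Conclusion.** The point holds as a minor wording defect. An unqualified instruction gives the wrong result at one scheduled visit and conflicts with Section 5.1.8. This rests on three conditions: a subject forgets the bottle at Visit 3, the visit is within its window, and the site follows the text literally. The further consequences depend on the day of the visit, on how the stop is logged and on whether it is corrected, as set out above.

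The documents give no rate of forgotten bottles, and it is probably low. A reader might infer that the main analysis or the power is at risk. That does not follow: one loss in an arm of 12 lies within the 10% allowance, the FAS analysis keeps the subject, and no stated power figure changes.

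**What to change.** In Section 5.1.7.1, limit the do-not-take instruction to visits at which replacement treatment is dispensed (Visits 4 and 5) and to EOT. Then add a sentence such as: *At Visit 3, where no new bottle is issued, a subject who has forgotten the current bottle continues dosing from it, takes that day's dose later the same day, and brings the bottle to the following visit for the count.* This fits Section 5.1.2, under which the dose follows the pre-dose assessments, and the same-day rule in Section 5.1.8.

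The cost is one or two sentences in the protocol and matching site instructions. No extra visit or drug supply is needed. The capsule count for a subject who forgot the bottle is made at Visit 4 instead of Visit 3.
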